7.4 Derived Data

Body Mass Index (BMI)

- BMI = $\{(Weight\ in\ kg)/(Height\ in\ m)^2\}$, if units are in kg for weight and m for height OR;
- BMI = $\{(Weight\ in\ lbs) \times 703.07\})/(Height\ in\ inches)^2\}$, if units are in lbs for weight and inches for height (Adjustments made to formula to standardize BMI unit to kg/m²).

Change from baseline

Change from baseline (preoperative) scores to postoperative time points (i.e. Visit_i) for all pertinent endpoints would be calculated at follow-up visits as follows:

Postoperative visit_i score – preoperative score.

Hip Disability and Osteoarthritis Outcome Score (HOOS)

The HOOS consists of 3 subscales; Pain, Stiffness and Function in daily living (ADL). Five standardized answer options are given and each question gets a score from 0 to 4. The detailed information is showed in Table 2. A normalized score (100 indicating no symptoms and 0 indicating extreme symptoms) for each subscale will be calculated as:

HOOS pain = 100 – AVERAGE (P1:P5)* 100/4

HOOS Stiffness = 100 – AVERAGE (S4:S5)* 100/4

HOOS ADL = 100 – AVERAGE (A1:A17)* 100/4

Table 2 HOOS Domain Questionnaire and Scores

HOOS Item #	HOOS Items (Individual item scores 0-4, with None = 0; Mild = 1; Moderate = 2; Severe = 3; Extreme = 4)
Pain (score range 0-20)	
P1	Walking on a flat surface?
P2	Going up or down stairs?
P3	At night while in bed?
P4	Sitting or lying?
P5	Standing upright?
Stiffness (score range 0-8)	
S4	Severity of stiffness after first wakening in the morning?
S5	Severity of stiffness after sitting/lying/resting later in the day?
ADL (score range 0-68)	
A1	Descending stairs?
A2	Ascending stairs?

CONFIDENTIAL AND PROPRIETARY

This document contains information that is confidential and proprietary to Smith & Nephew PLC and Smith & Nephew, Inc. and is intended for use only by Smith+Nephew and its manufacturer. It shall not be reproduced or copied in whole or in part, nor shall the contents be disclosed by any means without prior written permission from Smith+Nephew, nor shall anyone make any use of it that is contrary to the expressed or implied wishes of Smith+Nephew.

Statistical Analysis Plan

A prospective, multicenter, non-randomized, clinical outcomes study of the R3[◊] Acetabular System in patients with degenerative hip disease

Number:
R3H01/02/01/2017
ST: 1103
Version: 3.0
Page: 11 of 18

A3	Rising from sitting?
A4	Standing?
A5	Bending to floor/pick up an object?
A6	Walking on flat surface?
A7	Getting in/out of car?
A8	Going shopping?
A9	Putting on socks/stockings?
A10	Rising from bed?
A11	Taking off socks/stockings?
A12	Lying in bed?
A13	Getting in/out of bath/shower?
A14	Sitting?
A15	Getting on/off toilet?
A16	With heavy domestic duties?
A17	With light domestic duties?

If there are some missed answers, then the following rule will be followed.

1. For each subscale, if there are at least 50% of the items are answered, then we will calculate the subscale mean score as showed in Table 3.
2. For each subscale, if more than 50% of items are missed, then we will not calculate subscale mean score.
3. Subscale scores will be calculated independently, i.e. if a particular subscale is not valid, the results from the other subscale will still be calculated if available.

Table 3 Number of items needed for each subscale

SubDomain	# of items need to for calculation subscale mean score
Pain	3
Stiffness	1
ADL	9

Modified Harris Hip Score (HHS)

The mHHS includes a modification to the Harris Hip Score: the "Distance Walked" section of the Harris Hip Score was modified to replace the number of blocks with actual distances since the term "blocks" is not commonly used as a measurement of distance in Europe.

Table 4 displays the algorithms used for scoring each of the 10 items (components) of the mHHS as well as the domains (pain, function, AoD and ROM) of the mHHS and total mHHS.

Table 4. modified Harris Hip Score (HHS) scores per item and domain

CONFIDENTIAL AND PROPRIETARY

This document contains information that is confidential and proprietary to Smith & Nephew PLC and Smith & Nephew, Inc. and is intended for use only by Smith+Nephew and its manufacturer. It shall not be reproduced or copied in whole or in part, nor shall the contents be disclosed by any means without prior written permission from Smith+Nephew, nor shall anyone make any use of it that is contrary to the expressed or implied wishes of Smith+Nephew.

Statistical Analysis Plan

A prospective, multicenter, non-randomized, clinical outcomes study of the R3[◊] Acetabular System in patients with degenerative hip disease

Number:
R3H01/02/01/2017
ST: 1103
Version: 3.0
Page: 12 of 18

Item	Original Response	Likely scores per Item	Domains (Range of Scores)
Pain	None or ignores it	44	Pain Domain (0 to 44)
	Slight, minimal, no compromise in activities	40	
	Mild pain, no effect on average activities, rarely moderate pain with unusual activity; may take aspirin	30	
	Moderate pain; tolerable but makes concessions to pain. Some limitation of ordinary activity or work. May require occasional pain medication stronger than aspirin	20	
	Marked pain, serious limitation of activities	10	
	Totally disabled, crippled, pain in bed, bedridden	0	
Limp	None	11	Function Domain (0 to 47)
	Slight	8	
	Moderate	5	
	Severe	0	
Support	None	11	{Sum of all items within subdomain}
	Single cane for long walks	7	
	Single cane most of the time	5	
	One crutch	3	
	Two canes	2	
	Two crutches or not able to walk	0	
Distance walked	Unlimited	11	
	Six blocks	8	
	Daily shopping	5	
	Indoors only	2	
	Bed and chair only	0	
Sitting	Comfortably in ordinary chair	5	
	On a high chair for 30 minutes	3	
	Unable to sit comfortably in any chair	0	

CONFIDENTIAL AND PROPRIETARY

This document contains information that is confidential and proprietary to Smith & Nephew PLC and Smith & Nephew, Inc. and is intended for use only by Smith+Nephew and its manufacturer. It shall not be reproduced or copied in whole or in part, nor shall the contents be disclosed by any means without prior written permission from Smith+Nephew, nor shall anyone make any use of it that is contrary to the expressed or implied wishes of Smith+Nephew.

Statistical Analysis Plan

A prospective, multicenter, non-randomized, clinical outcomes study of the R3[◊] Acetabular System in patients with degenerative hip disease

Number:
R3H01/02/01/2017
ST: 1103
Version: 3.0
Page: 13 of 18

Public transportation	Yes, possible No, unable	1 0	
Stairs	Normally without using a railing Normally using a railing In any manner Unable to do stairs	4 2 1 0	
Socks/Shoes	With ease With difficulty Unable	4 2 0	
Range of Motion (ROM)	Flexion = FLEX+EXT-FLEX_ZERO Movement = ABD+ADD-ABD_ZERO Rotation = ER+IR-ER_ZERO	N/A N/A N/A	
ROM subscore	Flexion+Movement+Rotation 0 to 29 30 to 59 60 to 99 100 to 159 160 to 209 ≥ 209	0 1 2 3 4 5	Range of Motion Domain (0 to 5)
Leg Length Difference (in mm)	None Ipsilateral longer (LL_DIF_LONG) Ipsilateral shorter (LL_DIF_SHORT)	N/A N/A N/A	
Absence of Deformity (AOD)	IF (FLEX_ZERO = . OR FLEX_ZERO < 31) AND (ABD_ZERO = . OR ABD_ZERO < 11) AND (ER_ZERO = . OR ER_ZERO < 11) AND LL_DIF_LONG < 33 AND LL_DIF_SHORT < 33 THEN AODScore = 4	0 or 4	Absence of Deformity Domain (0 to 4)
Total HHS		Sum of all domain scores per subject	Sum of all domain scores per subject

CONFIDENTIAL AND PROPRIETARY

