7 STATISTICAL ANALYSIS

7.1 General

Smith+Nephew's Global Biostatistics group will conduct the statistical analysis for this study. Unless otherwise stated, all significance tests and hypothesis testing will be two-sided, performed at the 5% significance level. Resulting p-values will be quoted and 95% two-sided confidence intervals will be generated where appropriate. All p-values will be rounded to three decimal places, p-values less than 0.001 will be presented as '<0.001' in all tables.

CONFIDENTIAL AND PROPRIETARY

This document contains information that is confidential and proprietary to Smith & Nephew PLC and Smith & Nephew, Inc. and is intended for use only by Smith+Nephew and its manufacturer. It shall not be reproduced or copied in whole or in part, nor shall the contents be disclosed by any means without prior written permission from Smith+Nephew, nor shall anyone make any use of it that is contrary to the expressed or implied wishes of Smith+Nephew.

Statistical Analysis Plan

A prospective, multicenter, non-randomized, clinical outcomes study of the R3[◊] Acetabular System in patients with degenerative hip disease

Number:
R3H01/02/01/2017
ST: 1103
Version: 3.0
Page: 9 of 18

Where data summaries are specified, categorical and ordinal variables will be summarized with frequencies and percentages. Continuous variables will be summarized with the following summary statistics: number of observations, mean, median, standard deviation, minimum and maximum values. All analyses will be performed in SAS 9.4 (or later).

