7.3 Handling of Missing, Incomplete and Repeat Data

For the primary endpoint, subjects with hips that are prematurely discontinued from the study due to death or loss to follow-up would be censored on the last known date on-study.

Specific instructions for handling missing PROMs is described in Section 7.4. If $\geq 10\%$ of postoperative UCLA, HOOS or HHS scores at more than 2 of the postoperative follow-up time points are missing, only their observed data will be summarized using the change from preoperative to each postoperative time point as the endpoints of interest.

CONFIDENTIAL AND PROPRIETARY

This document contains information that is confidential and proprietary to Smith & Nephew PLC and Smith & Nephew, Inc. and is intended for use only by Smith+Nephew and its manufacturer. It shall not be reproduced or copied in whole or in part, nor shall the contents be disclosed by any means without prior written permission from Smith+Nephew, nor shall anyone make any use of it that is contrary to the expressed or implied wishes of Smith+Nephew.

Statistical Analysis Plan

A prospective, multicenter, non-randomized, clinical outcomes study of the R3[◊] Acetabular System in patients with degenerative hip disease

Number:
R3H01/02/01/2017
ST: 1103
Version: 3.0
Page: 10 of 18

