7.10 Analysis of Secondary Endpoints

- HOOS sub-scores, HHS (and its subscores) and UCLA would be summarized using descriptive summary characteristics for continuous variables at the preoperative and all postoperative time points. Changes from the preoperative (baseline) to subsequent postoperative visit(s) would also be summarized using descriptive statistics for continuous

CONFIDENTIAL AND PROPRIETARY

This document contains information that is confidential and proprietary to Smith & Nephew PLC and Smith & Nephew, Inc. and is intended for use only by Smith+Nephew and its manufacturer. It shall not be reproduced or copied in whole or in part, nor shall the contents be disclosed by any means without prior written permission from Smith+Nephew, nor shall anyone make any use of it that is contrary to the expressed or implied wishes of Smith+Nephew.

Statistical Analysis Plan

A prospective, multicenter, non-randomized, clinical outcomes study of the R3[◊] Acetabular System in patients with degenerative hip disease

Number:
R3H01/02/01/2017
ST: 1103
Version: 3.0
Page: 16 of 18

variables. Mixed Model Repeated Measures (MMRM) with a missing at random (MAR) assumption to account for the pattern of missing longitudinal data would be used to analyze the Patient Reported Outcome Measures (PROMs) to compare the scores between the preoperative and postoperative visit time points. The model will include fixed effect term for visit. The Kenward Rogers denominator degrees of freedom would be used coupled with a specification for an unstructured covariance matrix. The test of any of the comparisons between the preoperative and postoperative visits will be concluded to be statistically significant if $p < 0.05$. Model-based Means or Least Square (LS) Means for all visits as well as the differences between each postoperative versus the preoperative visit and their 95% two-sided Confidence Intervals (CI) would be presented. Should greater than 10% of any of the PROMs data on at least at two of the postoperative timepoints be missing, MMRM would not be used.

- For radiographic findings, patient satisfaction and Trendelenburg, descriptive summary statistics for categorical variables such as frequency (n) and percentage (%) will be presented by visit.

The secondary endpoint analysis will be performed only on the FAS population.

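### SAP Table 4 gives a hip with no examination data the full 4 Absence of Deformity points, and has no rule for the same blank fields in Range of Motion

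*SAP*

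**What the plan says.** Table 4 in SAP Section 7.4 scores the modified Harris Hip Score (mHHS) by domain. Two domains use the fields FLEX_ZERO, ABD_ZERO and ER_ZERO.

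- **AOD (0 or 4 points).** The rule begins "IF (FLEX_ZERO = . OR FLEX_ZERO < 31", continues with "ABD_ZERO = . OR ABD_ZERO < 11" and a matching condition for ER_ZERO, and ends "LL_DIF_LONG < 33 AND LL_DIF_SHORT < 33 THEN AODScore = 4". A blank contracture field passes by explicit instruction. The leg-length conditions have no term for a blank.
- **ROM (0 to 5 points).** Each component subtracts one of the same fields, for example "Flexion = FLEX+EXT-FLEX_ZERO". Nothing is said about a blank. The top two bands are printed as "160 to 209 ≥ 209".

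The total is the sum of the domain scores, and Table 4 has no rule for a missing domain. Section 7.3 tells the reader that "Specific instructions for handling missing PROMs is described in Section 7.4", but the visible text of 7.4 gives a missing-item rule for the HOOS only. Section 7.1 commits all analyses to SAS.

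**The concern.** The same blank field is handled in two ways. AOD reads it as no disqualifying contracture. ROM, taken as written, cannot be computed from it. AOD also never checks that any motion was measured.

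The mHHS is a secondary endpoint in SAP Section 5.2 and in Section 2.2 of the post-approval addendum. SAP Section 7.10 summarises its subscores as well as the total, by visit and as change from the preoperative value, so an AOD score given without data would appear directly in a reported result. If a missing ROM makes the total missing, the record also counts towards the 10% limits in Sections 7.3 and 7.10. Under the second of these, if too much is missing "on at least at two of the postoperative timepoints be missing, MMRM would not be used".

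Incomplete examinations are foreseeable. Protocol Section 7.5 and addendum Section 6.3 allow telephone follow-up that covers only device status and satisfaction. Any mHHS row created for such a contact would hold no examination data.

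**Working it through.** **Table 4's own ranges.** Function maximum: 11 + 11 + 11 + 5 + 1 + 4 + 4 = 47, as stated. All domains: 44 + 47 + 5 + 4 = 100. The table is internally sound on this.

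**SAS behaviour used.** A missing value compares as smaller than any number. The operators + and - return missing if any term is missing. The SUM() function ignores missing terms.

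**Illustrative hip (assumed values).** FLEX 110, EXT 10, ABD 40, ADD 25, ER 35, IR 25, leg-length difference 0 unless stated. With zeros entered in the three contracture fields the ROM sum is (110 + 10 - 0) + (40 + 25 - 0) + (35 + 25 - 0) = 245, which scores 5. With FLEX_ZERO = 40 it is 245 - 40 = 205, which scores 4, and AOD is 0 because 40 is not below 31.

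| Record | AOD | ROM with minus sign, as written | ROM with SUM() |
|---|---|---|---|
| All three contracture fields entered as 0 | 4 | 5 | 5 |
| FLEX_ZERO blank, other two 0 | 4 | missing | 5 |
| All three blank | 4 | missing | 5 |
| FLEX_ZERO blank, ABD_ZERO = 15 | 0 | missing | 5 |
| FLEX_ZERO = 40, other two 0 | 0 | 4 | 4 |
| Only the leg-length fields blank | 4 | 5 | 5 |
| Nothing examined, leg length blank | 4 | missing | missing |

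Three fields, each blank or 0, give 2 × 2 × 2 - 1 = 7 patterns with at least one blank. All 7 give AOD = 4 and ROM missing under the arithmetic as written. The fourth row shows that a blank does not earn the 4 points by itself; the other conditions must pass too. The last row does not depend on how ROM is coded.

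**Effect on the total for an unexamined hip.**

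- If domains are added with +, the total is missing and the 4 points never enter it.
- If they are added with SUM(), a hip whose true scores are AOD 4 and ROM 5 comes out 5 points too low. A hip with true AOD 0 and true ROM r changes by 4 - r: +1 for r = 3, 0 for r = 4, -1 for r = 5.

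**Effect on a visit mean.** The AOD shift is 4 × (share of records blank) × (share of those whose true AOD is 0). The blank rate is not in the documents. At assumed rates of 5%, 10%, 20% and 30%, with the last factor at its maximum of 1, the ceilings are 0.2, 0.4, 0.8 and 1.2 points. If a missing ROM is summed as 0, the largest loss at the same rates is 5 × rate: 0.25, 0.5, 1.0 and 1.5 points.

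**Band boundary.** A ROM sum of exactly 209 falls in both the 4-point and the 5-point band.

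**The case against.** The strongest reply is that the ROM rows define quantities and are not SAS code. They are silent on blanks. A programmer who uses SUM(), or sets blanks to 0, gets ROM 5 for the illustrative hip, in line with AOD. The explicit test for a blank in AOD is redundant in SAS, because a missing value is already below 31, so it looks deliberate and suggests that blank was meant as no contracture. A hip with no leg-length difference may likewise leave both length fields blank. The CRF would settle this, but it is not among the documents, and text directly after Table 4 could not be checked and may hold an mHHS rule.

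Much of this stands, and it rules out three stronger readings that a reader might infer.

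- *One of the two rules must be wrong whatever the CRF convention.* Not supported. If the CRF requires a 0 to be entered and blanks never occur, neither rule errs. If blank means no contracture and ROM is coded accordingly, both are right for examined hips.
- *The total mHHS is biased upward.* Not shown. ROM is lost on the same records, so the total may be missing, too low, unchanged or too high.
- *Visit means shift by 0.2 to 1.2 points.* These are ceilings at assumed blank rates, reached only if every blank hip would truly score AOD 0.

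The reply does not reach the unexamined record. It scores AOD 4 of 4 however ROM is coded, and a recode of blanks to 0 without a check that motion was recorded would leave that in place.

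**Conclusion.** The point holds in a limited form. Table 4 states a rule that credits 4 of 4 AOD points to a record with no examination, and leaves the same blanks undefined in ROM. Under the arithmetic as printed, ROM becomes missing for that record and also for an examined hip with blank contracture fields. Per hip and visit, at most 4 points (AOD) and 5 points (ROM) of 100 are involved, or the whole total if a missing domain makes it missing.

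This rests on SAS comparison and operator rules and on blanks actually occurring. Their frequency is unknown, so crossing a 10% missing-data limit is a possibility only. The finding concerns one secondary endpoint and its reported subscores; survivorship, the primary endpoint, is unaffected. The overlap at 209 is a minor slip that affects one value by one point. The correction should be made before the mHHS is derived.

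**What to change.** Amend Table 4 and the derivation code as follows.

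1. State what a blank contracture field means on the CRF. Where the corresponding motion fields are recorded and the CRF confirms that blank means no contracture, set the blank to 0 in both ROM and AOD.
2. Where no motion is recorded, set both ROM and AOD to missing.
3. Require a recorded leg-length answer (none, longer or shorter) before awarding the 4 AOD points.
4. State how the total is formed when a domain is missing. Setting it to missing is one option, but this discards records with complete pain and function scores (44 + 47 = 91 of 100 points) and adds to the missingness counted in Sections 7.3 and 7.10. The choice should be made openly.
5. Remove the overlap at a ROM sum of 209.

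The cost is one table edit and a few lines of code. The downside is that some records now scored on AOD become missing.

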7.5 Baseline Data

The following preoperative, operative and demographic variables would be summarized using descriptive characteristics for continuous¹ or categorical² data as appropriate:

- Age¹ (in years),
- Sex² (males or females),
- Height¹ (in cm),
- Weight¹ (in kg),
- BMI¹
- Primary diagnosis²,
- Charnley classification²
- Surgical history ipsilateral²
- ASA Physical Status²
- Head, Size, Neck Length, Inlay Material, Inlay²
- Surgical Approach²

Variables summarized will not only be restricted to the above listed but all variables deemed pertinent and obtainable preoperatively and operatively.

7.6 Disposition Data

Hip accountability will be summarized by study visit (see Table 1 for visit schedule) for the number of hips that are theoretically due, subjects who died, hips that were revised, hips terminated from the study for any reason. Additional information will include but not limited to number of subjects presenting at each visit, number of hips expected at each visit and follow up rate.

7.7 Protocol Deviations

A listing of all protocol deviations encountered on-study will be summarized.

CONFIDENTIAL AND PROPRIETARY

This document contains information that is confidential and proprietary to Smith & Nephew PLC and Smith & Nephew, Inc. and is intended for use only by Smith+Nephew and its manufacturer. It shall not be reproduced or copied in whole or in part, nor shall the contents be disclosed by any means without prior written permission from Smith+Nephew, nor shall anyone make any use of it that is contrary to the expressed or implied wishes of Smith+Nephew.

Statistical Analysis Plan

A prospective, multicenter, non-randomized, clinical outcomes study of the R3[◊] Acetabular System in patients with degenerative hip disease

Number:
R3H01/02/01/2017
ST: 1103
Version: 3.0
Page: 15 of 18

7.8 Multiplicity

No adjustments for multiplicity are planned for this study.

7.9 Analysis of Primary Endpoint

The Kaplan-Meier survival estimate would be used to estimate implant survivorship. Time to device revision will be the endpoint of interest to estimate the implant survivorship. Implant survival time (in months) is computed as: (Event Date – Operative Date+1)/30.4375.

Implanted hips that continue until study completion without an on-study revision will be censored at their last known date of participation in the study. Any premature hip discontinuation from study due to a subject's death or any other reason will be censored on the date of this discontinuation. A subject who is lost to follow-up will be censored at the subject's last known contact date. The Cumulative proportion of implant survivorship at 36 months (3-year), 60 months (5 years), 84 months (7 years) and 120 months (10 years) will be estimated and displayed accordingly. These Kaplan-Meier estimates will be provided with their corresponding two-sided 95% Confidence Intervals (CIs). If feasible, Kaplan-Meier survival graphs will be displayed to graphically illustrate implant survivorship over the study duration.

For the a-priori protocol-specified hypothesis, if the lower bound of 95% two-sided CIs at 3 years, 5 years, 7 years and 10 years are not less than 97%, 95%, 93% and 90% respectively, then we conclude that implant survivorship of the R3 cup is at least 97% at 3 years, 95% at 5 years, 93% at 7 years, and 90% at 10 years follow-up respectively.

The primary endpoint analysis will be performed on the FAS population. As sensitivity analysis, the same analysis will be performed on the PP population.

7.10 Analysis of Secondary Endpoints

- HOOS sub-scores, HHS (and its subscores) and UCLA would be summarized using descriptive summary characteristics for continuous variables at the preoperative and all postoperative time points. Changes from the preoperative (baseline) to subsequent postoperative visit(s) would also be summarized using descriptive statistics for continuous

CONFIDENTIAL AND PROPRIETARY

This document contains information that is confidential and proprietary to Smith & Nephew PLC and Smith & Nephew, Inc. and is intended for use only by Smith+Nephew and its manufacturer. It shall not be reproduced or copied in whole or in part, nor shall the contents be disclosed by any means without prior written permission from Smith+Nephew, nor shall anyone make any use of it that is contrary to the expressed or implied wishes of Smith+Nephew.

Statistical Analysis Plan

A prospective, multicenter, non-randomized, clinical outcomes study of the R3[◊] Acetabular System in patients with degenerative hip disease

Number:
R3H01/02/01/2017
ST: 1103
Version: 3.0
Page: 16 of 18

variables. Mixed Model Repeated Measures (MMRM) with a missing at random (MAR) assumption to account for the pattern of missing longitudinal data would be used to analyze the Patient Reported Outcome Measures (PROMs) to compare the scores between the preoperative and postoperative visit time points. The model will include fixed effect term for visit. The Kenward Rogers denominator degrees of freedom would be used coupled with a specification for an unstructured covariance matrix. The test of any of the comparisons between the preoperative and postoperative visits will be concluded to be statistically significant if $p < 0.05$. Model-based Means or Least Square (LS) Means for all visits as well as the differences between each postoperative versus the preoperative visit and their 95% two-sided Confidence Intervals (CI) would be presented. Should greater than 10% of any of the PROMs data on at least at two of the postoperative timepoints be missing, MMRM would not be used.

- For radiographic findings, patient satisfaction and Trendelenburg, descriptive summary statistics for categorical variables such as frequency (n) and percentage (%) will be presented by visit.

The secondary endpoint analysis will be performed only on the FAS population.

